6.3.1 Dose Adjustment Guidelines for Selinexor Related Toxicities

Toxicity will be graded according to NCI CTCAE, version 4.03; the therapy modifications described below are applied according to this severity grading.

If more than one different type of toxicity occurs concurrently, the most severe grade will determine the modification.

Re-escalation of the study drug is allowed as outlined in the sections that apply for the specific toxicity. If drug-related toxicity requires a treatment delay of more than 28 days the patient is taken off protocol treatment.

Each dose modification or treatment delay has to be documented, including the respective reason.

Table 2: Prespecified dose/schedule modifications for adverse events related to study drug

Dose level	Dose of Selinexor
Dose level 0	60 mg twice weekly (D1, D3)
Dose level -1	50 mg twice weekly (D1, D3)
Dose level -2	40 mg once weekly (D1)
Dose level -3	30 mg once weekly (D1)
Dose level -4	Discontinue dosing

Based on observations from the ongoing Phase 1 studies in patients with advanced hematological and solid tumors, we note that selinexor shows a reasonably wide therapeutic range, with activities from $\sim 10\text{mg}/\text{m}^2$ to $\geq 50\text{mg}/\text{m}^2$. Therefore, in order to optimize specific anti-tumor activity and the patient's tolerability, we will allow for dose and/or schedule modifications as described below. Patients should also be treated aggressively with supportive care to reduce toxicities.

Table 3: Criteria for dose adjustments of Selinexor-related toxicities

Toxicity and Intensity	Dose Modification
Fatigue (common)	
Grade 1	Insure adequate caloric intake and assess volume status. Adjust other medications. Consider addition of low dose corticosteroids (e.g., 4 mg dexamethasone with each dose of Selinexor or 10 mg prednisone per day every day). Rule out other causes of fatigue such as adrenal insufficiency.
Grade 2	Insure adequate caloric and fluid intake and assess volume status. Add corticosteroids on day of Selinexor (e.g., 4 mg dexamethasone), or give or 10-15mg prednisone every other day. If fatigue dose not resolve to Grade 1, increase corticosteroids to the day of and the day after Selinexor dosing, and/or reduce dose of Selinexor by one level (Table 2).

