Grade 2 lasting \geq 7 days and Grade 3	Insure adequate caloric and fluid intake and assess volume status. Interrupt Selinexor dosing until resolved to Grade \leq 1, reduce dose of Selinexor by 1 level (Table 2), and add corticosteroids on day of (\pm day after) Selinexor dosing.
Anorexia or weight loss (common)	
Grade 1	Assess dietary options (e.g., try a variety of other foods). Add high-calorie supplements (e.g., Ensure [®]). If fatigue or nausea also present, consider low doses of corticosteroids (as for fatigue) on day of \pm day after Selinexor dosing.
Grade 2	Add high-calorie supplements (e.g., Ensure [®]). Consider olanzapine 2.5-5 mg po qhs (especially if nausea or sleep disturbance present). Consider megestrol acetate 400-800 mg daily. Consider low dose corticosteroids (see fatigue). Consider anabolic steroids such as oxandrolone. Consider dronabinol (Marinol [®]). Skip intermittent doses of Selinexor while supportive medications are instituted. If Grade 2 anorexia does not resolve after institution of supportive medications, reduce Selinexor dose by 1 level (Table 2).
Grade 3	Interrupt dosing with Selinexor. Add high calorie supplements. Use supportive medications alone or in combinations. Restart Selinexor at 1 dose level reduction (Table 2) once anorexia resolves to Grade \leq 2 and weight stabilized. If Grade 2 anorexia persists with supportive medications, reduce dose of Selinexor another level (Table 2).
Nausea/Emesis (common)	
Grade 1	5-HT3 antagonists, D2 antagonists, olanzapine 5mg qhs or 2.5mg bid, corticosteroids (e.g., 4-10 mg dexamethasone with each dose of Selinexor \pm the day after dosing), NK1 antagonists, or dronabinol (Marinol) or combinations can prevent nausea in the majority of patients.
Grade 2	Implement one or more combinations of anti-nausea medications. If nausea does not resolve to Grade \leq 1, reduce dose of Selinexor by one dose level (Table 2).

Toxicity and Intensity	Dose Modification
Grade 3	Implement one or more combinations of anti-nausea medications and interrupt dosing of Selinexor. Selinexor may be restarted with one dose level reduction (Table 2) when nausea is Grade \leq 2 and adequate caloric and fluid intake have been achieved.
Hyponatremia (common)	

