Grade 1 (Lower Limit of Normal to 130 nM)	Maintain dose level, assure adequate fluid, electrolyte and caloric intake, adjust other medications, consider salt supplementation, rule out other causes. Be certain that reported sodium level is corrected for concurrent hyperglycemia (serum glucose $>$ 150mg/dL).
Grade 3 (120-130 nM) without symptoms	First Occurrence: Discontinue Selinexor until resolved to Grade \leq 1 then reinstate starting dose. Check renal function, serum and urinary electrolytes, and rule out other causes. Reinforce patient education regarding fluid intake. Be certain that reported sodium level is corrected for concurrent hyperglycemia (serum glucose $>$ 150mg/dL). Subsequent Occurrences: Discontinue Selinexor until resolved to Grade \leq 1 then reduce dose by 1 level (Table 2). Check renal function, serum and urinary electrolytes, and rule out other causes.
Grade 3 (120-130 nM with symptoms) or Grade 4 (<120 nM)	Check renal function, serum and urinary electrolytes, and rule out other causes. Be certain that reported sodium level is corrected for concurrent hyperglycemia (serum glucose $>$ 150mg/dL). Discontinue Selinexor until resolved to Grade \leq 1 then reduce dose by 1 level (Table 2). Check renal function, serum and urinary electrolytes, and rule out other causes.
Renal (rare)	
Serum creatinine	
Calculated or measured creatinine clearance \geq 20 cc/min	Maintain dose level
Calculated or measured creatinine clearance $<$ 20 cc/min	Maintain dose level as Selinexor is not eliminated by the kidney.
Hepatic (rare)	
Bilirubin	
Total bilirubin $<$ 1.5 x ULN	Maintain dose level
Total bilirubin 1.5-3 x ULN	Reduce Selinexor to once weekly dosing at the same dose until resolved to \leq Grade 1, then restart twice weekly dosing

Toxicity and Intensity	Dose Modification

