Grade 2 / 3	
Delay Selinexor and initiate/intensify antihypertensive therapy. Selinexor may be restarted in conjunction with standard anti-hypertensive medication if BP is controlled (i.e., BP \leq 150/100 mmHg).
 
If BP is controlled \leq 7 days after suspending Selinexor, maintain dose level
 
If BP is controlled $>$ 7 days after suspending Selinexor, then reduce by 1 dose level (Table 2).

Grade 4	
Delay the Selinexor and initiate/intensify antihypertensive therapy, then reduce by 1 dose level (Table 2).
 
Selinexor may be restarted in conjunction with anti-hypertensive medication if BP is controlled (i.e., BP \leq 150/100 mmHg).

Cardiac – Other (rare)	
Grade 1 or 2	Maintain dose level
Grade 3	Delay Selinexor until resolved to \leq Grade 1, then reduce by 1 dose level (Table 2).
Grade 4	Discontinue study treatment
Diarrhea (common)	
Grade 1 (despite maximal anti-diarrheal medication)	At the first sign of abdominal cramping, loose stools, or onset of diarrhea, it is recommended that the patient be treated according to institutional standard of care. Maintain dose level of Selinexor.
Grade 2 (despite maximal anti-diarrheal medication)	
Reduce to Selinexor to one weekly until resolved to \leq Grade 1, then re-start twice weekly at the current dose level.
 
If diarrhea returns as \geq Grade 2, then reduce Selinexor dose by one dose level and dose once weekly until resolved to \leq Grade 1, then re-start twice weekly at reduced dose level

Grade 3/4 (despite maximal anti-diarrheal medication)	Delay Selinexor until resolved to \leq Grade 1 or baseline and patient is clinically stable, then follow guidelines above.
Neurotoxicity (not observed to date)	
\geq 1 CTCAE grade level increase	
Grade 0 \rightarrow Grade 1: maintain dose level
 
Grade 0 or 1 \rightarrow Grade 2: delay study treatment until resolved to \leq Grade 1, then reduce by 1 dose level (Table 2).

\geq CTCAE Grade 3	Discontinue study treatment until resolved to Grade \leq 1 then reduce by 2 dose levels (Table 2).
Amylase and/or lipase elevations (rare)	
Grade 1 or 2	Maintain dose level

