Asymptomatic Grade 3 or 4	
Delay Selinexor until \leq Grade 2, then restart at 1 dose level reduction (Table 2). Rule out other causes of amylase/lipase elevation. If levels have not returned to \leq Grade 2 within 3 weeks then no further Selinexor may be given and the patient should discontinue permanently from the study. A computed tomography (CT) scan or other imaging study to assess the pancreas, liver and gallbladder must be performed within 1 week of the first occurrence of any Grade 3 elevation of amylase and/or lipase.

Toxicity and Intensity	Dose Modification
Symptomatic Grade 3 or 4	Selinexor must be stopped immediately and proper supportive care provided. Evaluate enzyme levels at least twice weekly until resolution to ≤ Grade 1. Clinical manifestations should be monitored as needed until resolution or stabilization of the disease condition. Selinexor may be re-started at 2 dose levels below (Table 2) after resolution to ≤ Grade 1.
Pancreatitis (not observed to date)	
Grade 1	Maintain dose level
Grade 2, 3 or 4	Discontinue study treatment.
Thrombocytopenia	
Grade 1 or 2	Maintain dose. Rule out other causes including drug effects.
Grade 3 without bleeding	Rule out other causes including drug effects. For first occurrence: continue dosing without interruption: however, reduce Selinexor by 1 dose level. For ≥ second occurrence: interrupt selinexor and check platelet counts weekly until recovers to Grade 2 or baseline and reduce selinexor by 1 dose level. If the occurrence falls on a Day 1 of a cycle: delay start of cycle, check platelet counts weekly until recovers to Grade 2 or baseline and reduce selinexor by 1 dose level when resuming.
Grade 4 without bleeding	Rule out other causes including drug effects. Interrupt Selinexor until recovers to Grade 2 or baseline and reduce selinexor by 1 dose level. If the occurrence falls on a Day 1 of a cycle: delay start of cycle, check platelet counts weekly until recovers to Grade 2 or baseline and reduce selinexor by 1 dose level when resuming.

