≥ Grade 3 with bleeding	Interrupt selinexor dosing and check platelet counts weekly until the bleeding has stopped, patient is clinically stable and the platelets have recovered to Grade 2 or baseline. When resuming selinexor, reduce by 1 dose level. If the occurrence falls on a Day 1 of a cycle: delay start of cycle, check platelet counts weekly until the bleeding has stopped, patient is clinically stable and the platelets have recovered to Grade 2 or baseline. Reduce selinexor by 1 dose level when resuming.
Neutropenia	
Grade 3 or 4 Neutropenia With (febrile neutropenia) OR Without fever	Institute prophylactic antibiotics as clinically indicated per institutional guidelines. Interrupt selinexor and check neutrophils weekly until recovers to Grade 2 or baseline and without fever (if febrile) and the patient is clinically stable. Reduce selinexor by 1 dose level when resuming. If the occurrence falls on a Day 1 of a cycle: delay start of cycle, check neutrophils weekly until recovers to Grade 2 or baseline and without fever (if febrile) and the patient is clinically stable. Reduce selinexor by 1 dose level when resuming.
Anemia	
Treat per institutional guidelines including blood transfusion. Consider transfusing for haemoglobin < 8 g/dL. If possible, maintain selinexor dose as long as patient is clinically stable, but if a dose reduction or interruption is desired, consult with the Medical Monitor.	

Toxicity and Intensity	Dose Modification
Other Selinexor-related adverse events	
Grade 1 or 2	Maintain dose level and initiate standard supportive care.
Grade 3	Delay dose until resolved to ≤ Grade 1, then reduce by 1 dose level (Table 2).
Grade 4	Discontinue Selinexor and rule out other causes. If other causes of Grade 4 adverse event are uncovered, Selinexor may be re-initiated at 1 dose level reduction (Table 2).

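### When Selinexor-related toxicities coincide, choosing the action by highest grade can cancel a stricter Table 3 action for a lower-grade toxicity that resolves first

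*Protocol*

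**What the plan says.** Protocol 6.3.1 gives one rule for overlapping toxicities: "If more than one different type of toxicity occurs concurrently, the most severe grade will determine the modification". Table 3 gives the action for each toxicity, and the dose-level table in the same section (Table 2) gives the doses. These rows matter here:

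- **Neurotoxicity, Grade 3 or higher:** stop until Grade 1 or lower, "then reduce by 2 dose levels (Table 2").
- **Neutropenia, Grade 3 or 4:** "Interrupt selinexor and check neutrophils weekly until recovers to Grade 2 or baseline and without fever (if febrile) and the patient is clinically stable"; then "Reduce selinexor by 1 dose level when resuming".
- **Thrombocytopenia, Grade 4 without bleeding:** "Interrupt Selinexor until recovers to Grade 2 or baseline and reduce selinexor by 1 dose level".
- **Fatigue, Grade 2 for at least 7 days, or Grade 3:** hold until Grade 1 or lower, then "reduce dose of Selinexor by 1 level (Table 2), and add corticosteroids on day of" dosing.
- **Diarrhea, Grade 3 or 4:** hold until Grade 1 or lower (or baseline) and stable, then refer back to the preceding diarrhea guidance.
- **Pancreatitis, Grade 2 to 4:** discontinue study treatment, with no restart criterion.

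A closing note to Table 3 bases modifications on the worst preceding toxicity. Section 6.3.4 lists exceptions, including reversible electrolyte abnormalities.

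**The concern.** A highest-grade rule protects the patient only if a higher grade of one toxicity always carries an action at least as strict as a lower grade of another. Table 3 was written toxicity by toxicity and lacks that property. Where the order is reversed, a site that follows 6.3.1 to the letter, as 6.2.3 asks, gives more Selinexor on resumption than the lower-grade row would allow.

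The neurotoxicity row matters most. Section 1.1.2.2 reports cerebellar neuron changes in animals at high repeated doses, and 7.1.5 makes acute cerebellar syndrome an event of special interest. The two-level cut is the protocol's own safeguard, and the rule can switch it off.

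**Working it through.** The documents give no figure to reproduce. The check compares Table 3 rows and converts dose levels to weekly dose.

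**Weekly dose by level (6.3.1, Table 2).** Level 0: 2 × 60 = 120 mg. Level -1: 2 × 50 = 100 mg. Level -2: 40 mg. Level -3: 30 mg. Level -4: 0 mg. With dosing in weeks 1 to 3, multiply by 3 for a 4-week cycle.

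**Main example: Grade 3 neurotoxicity with Selinexor-related Grade 4 neutropenia (or Grade 4 thrombocytopenia without bleeding).** The outcome depends on which resolves first.

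- *Neutrophils recover first.* The remaining neurotoxicity becomes the most severe toxicity, so its own hold applies. If it is still Grade 3, so does its two-level cut. The rule does no harm.
- *Neurotoxicity falls to Grade 1 or lower first, while the cytopenia is still Grade 4.* The cytopenia row has governed throughout. On recovery, Selinexor resumes one level down and the two-level cut is never triggered.
- *The cytopenia eases to Grade 3 while neurotoxicity is still Grade 3.* The grades tie, and the sentence gives no answer.

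For the second sequence:

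| Level before the event | One level down (rule as written), mg/week | Two levels down (neurotoxicity row), mg/week | Per cycle, mg |
|---|---|---|---|
| 0 | 100 | 40 | 300 vs 120 |
| -1 | 40 | 30 | 120 vs 90 |
| -2 | 30 | 0 | 90 vs 0 |
| -3 | 0 | 0 | no difference |

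From level 0 the ratio is 100/40 = 2.5.

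**Second example: fatigue with diarrhea.** Grade 2 fatigue reaches 7 days during a hold for a first Grade 3 or 4 diarrhea episode and clears before the hold ends. The diarrhea row governs. If its reference back means keeping the current level, Selinexor resumes from level 0 at 120 mg/week, against 100 mg/week under the fatigue row.

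**Third example: Grade 2 or 3 pancreatitis with Selinexor-related Grade 4 neutropenia.** The neutropenia row governs: hold, then one level down. If the pancreatitis resolves first, Selinexor resumes from level 0 at 100 mg/week, against 0 under the pancreatitis row.

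**Who could still be exposed under version 3.1 (13.01.2017).** Enrolment ended in June 2016 (3.2). Assume the last registration was on 30 June 2016 and treatment started 14 days later, on 14 July 2016.

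- One-year cap counted from first dose: ends 14 July 2017, which is 182 days after the version date.
- One-year cap counted after two 28-day induction cycles (14 July + 56 days = 8 September 2016): ends 8 September 2017, which is 238 days after the version date.

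By January 2017 induction would long have been over. Any remaining patients would be in late consolidation or maintenance.

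**The case against.** **Other text lets a site do better.** Section 6.3 permits flexible reductions, 5.4 allows removal for a health hazard, and the worst-preceding-toxicity note could be read as clinical judgement. All true, but none of these requires the stricter row, and the note reads most naturally as the same severity ranking.

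**The events are rare or outside Table 3.** The row headings say that neither neurotoxicity nor pancreatitis had been seen so far. Section 6.3.1 treats Grade 3 or higher events not related to Selinexor separately, which takes out cytopenia due to chemotherapy alone. This stands, and it limits the size of the point. It does not remove it: Appendix 2 sets a low bar for relatedness, and in maintenance Selinexor is given without Ara-C once consolidation is over.

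**Stronger readings that the documents do not support.**

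- *Dosing may resume before neurotoxicity has resolved.* A reader might infer this from the laxer neutropenia criterion. But once neutrophils recover, a continuing neurotoxicity is the most severe toxicity left, and its own row requires waiting for Grade 1 or lower.
- *Grade 2 anorexia or nausea loses its dose cut.* The anorexia row says "If Grade 2 anorexia does not resolve after institution of supportive medications, reduce Selinexor dose by 1 level (Table 2"), and the nausea row is built the same way. If the symptom outlasts the higher-grade event, the cut is still due. If it clears, the trigger is gone. If the trigger was met earlier, the cut was due then.
- *Asymptomatic Grade 3 hyponatremia is a common route to the problem.* Its first-occurrence row does say "then reinstate starting dose. Check renal function, serum and urinary electrolytes, and rule out other causes", and 6.5.7 reports frequent Grade 3 cases with gastrointestinal symptoms. But 6.3.4 exempts electrolyte abnormalities that standard measures reverse, and 6.5.7 says all those cases were quickly corrected. The counts there do not measure how often this rule misfires.

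**Conclusion.** The point holds in a narrow form. The rule can cancel a stricter required action when the lower-grade toxicity resolves before the higher-grade one. In the main case Selinexor resumes from level 0 at 2.5 times the weekly dose that the neurotoxicity row allows.

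This assumes that both toxicities are judged related to Selinexor and that the higher-grade one keeps the higher grade until the other has cleared. The diarrhea example also depends on how the reference back is read. The pancreatitis example takes discontinuation as permanent, since the row gives no restart criterion.

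The documents give no frequency for these combinations, and none is claimed. They are uncommon, and few patients could still be exposed under version 3.1. No endpoint, sample size or analysis is affected. This is a minor dosing-safety correction.

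**What to change.** Replace the sentence in 6.3.1, by amendment, with:

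> If more than one type of Selinexor-related toxicity occurs concurrently, each applicable Table 3 row is applied, including the row of a toxicity that resolves before the others. Any row requiring permanent discontinuation prevails. Otherwise Selinexor is held until the resumption criteria of every applicable row that calls for a hold are met, and is resumed at the lowest weekly dose that any applicable row requires. The exceptions in 6.3.4 apply.

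Align the closing note to Table 3 with this.

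Checks from level 0:

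- Grade 3 neurotoxicity with Grade 4 neutropenia: hold until both criteria are met, then 40 mg/week.
- Prolonged Grade 2 fatigue with Grade 3 or 4 diarrhea: hold until both criteria are met, then 100 mg/week.
- Pancreatitis with Grade 4 neutropenia: stop.

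The wording also settles equal-grade ties.

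The cost is one sentence and one note. Section 12 requires authority and ethics approval for a substantial amendment, so the change is best bundled with another one while patients are still on Selinexor. No procedures are added. A few patients would receive slightly less Selinexor, and joint hold criteria might bring a few more to the 28-day limit for coming off treatment.

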Grade 3 ($> 3.0-10.0 \times \text{ULN}$) Grade 4 ($> 10.0 \times \text{ULN}$)	
Discontinue Selinexor until resolved to Grade ≤ 2, then follow guidelines above.
 
Note: If Grade 3 or Grade 4 hyperbilirubinemia is due to the indirect component only, and hemolysis as the etiology has been ruled out as per institutional guidelines (e.g. review of peripheral blood smear and haptoglobin determination), then reduce Selinexor dose by 1 level (Table 2) and continue treatment at the discretion of the investigator.
 
Discontinuation of Selinexor is required if concurrent elevations of total bilirubin $> 2.0 \times$ upper limit of normal (ULN) and ALT or AST $> 3.0 \times$ ULN are observed and other causes have been ruled out.
 
In order to characterize hepatic toxicity more precisely, fractionation of bilirubin and alkaline phosphatases will be required for elevated values $> 2.0 \times$ ULN and \geq CTCAE Grade 2, respectively.

AST or ALT (rare)	
Grade 1 ($> \text{ULN}-2.5 \times \text{ULN}$)	Maintain dose level
Grade 2 ($> 2.5-5.0 \times \text{ULN}$)	Delay Selinexor until resolved to Grade ≤ 1 , then maintain dose level. Consider addition of S-adenosylmethionine (SAM) 400mg qd-bid.
Grade 3 ($> 5.0-20.0 \times \text{ULN}$)	
Delay Selinexor until resolved to \leq Grade 2, then reduce by 1 dose level (Table 2).
 
Consider addition of S-adenosylmethionine (SAM) 400mg qd-qid.
 
If no further AST or ALT elevations occur during one cycle (4 weeks) at the reduced dose level, then dose may be continued at the reduced dose.
 
Discontinuation of Selinexor is required if concurrent elevations of direct bilirubin $> 2.0 \times$ upper limit of normal (ULN) and ALT or AST $> 3.0 \times$ ULN are observed.
 
In order to characterize hepatic toxicity more precisely, fractionation of bilirubin and alkaline phosphatases will be required for elevated values $> 2.0 \times$ ULN and \geq CTCAE Grade 2, respectively.

Grade 4 ($> 20.0 \times \text{ULN}$)	Delay Selinexor until resolved to \leq Grade 2, then reduce by 2 dose levels (Table 2).
Cardiac (rare)	
Hypertension	Treatment-emergent hypertension should be treated as per standard cardiology practice. Recommended agents for the management of blood pressure elevations on Selinexor include angiotensin-converting enzyme inhibitors and calcium channel blockers.
Grade 1	Maintain dose level

Toxicity and Intensity	Dose Modification

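### Recurrent diarrhea from dose level -1 down: the Table 3 restart frequency contradicts the Table 2 dose level (80 versus 40 mg/week at the first step affected)

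*Protocol*

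**What the plan says.** Section 6.3.1 of the protocol contains a dose-level table (its Table 2, not the schedule of assessments that carries the same number) and a table of actions by toxicity (Table 3).

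- **Table 2.** Level 0 is 60 mg twice weekly. Level -1 is "50 mg twice weekly (D1, D3"). Level -2 is "40 mg once weekly (D1"). Level -3 is 30 mg once weekly, and level -4 is discontinuation.
- **Table 3, Grade 2 diarrhea, first episode.** Go to once weekly until Grade 1 or less, "then re-start twice weekly at the current dose level".
- **Table 3, diarrhea returning at Grade 2 or higher.** Go down one dose level, dose once weekly until Grade 1 or less, "then re-start twice weekly at reduced dose level".
- **Table 3, bilirubin 1.5 to 3 times the upper limit of normal.** Go to once weekly at the same dose until Grade 1 or less, "then restart twice weekly dosing".
- **Table 3, Grade 3/4 diarrhea and bilirubin.** Interrupt Selinexor, "then follow guidelines above".

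Some other rows reduce by two levels in one event: Grade 4 AST/ALT ("then reduce by 2 dose levels (Table 2")) and symptomatic amylase/lipase elevation ("Selinexor may be re-started at 2 dose levels below (Table 2")).

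**The concern.** The recurrence sentence takes the level from Table 2 but sets its own frequency. That works only where the reduced level is itself twice weekly, which holds for level -1 and for no level below it. A patient at level -1 whose diarrhea recurs goes to level -2. The row then says twice weekly, while the definition of that level says once weekly.

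No unusual history is needed. The diarrhea row can lead there alone: a first episode at level 0 keeps the level, a recurrence leads to -1, and a further recurrence leads to -2.

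At stake is dosing consistency in patients who have already shown toxicity. Two sites could each claim to follow the protocol and give weekly doses that differ by a factor of two. From level -2, the row as written restarts above the Table 2 dose that the patient held before the event.

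**Working it through.** **Inputs.** Milligrams and frequency per level come from Table 2 in section 6.3.1, and the restart frequency from the Table 3 rows. There are three dosing weeks per 4-week cycle (section 3.1.2).

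**Formula.** Weekly dose = mg per dose × doses per week. Cycle dose = weekly dose × 3.

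**Check on the plan's own schedule.** Level 0 gives 2 × 3 = 6 doses per cycle, as section 3.1.2 states.

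**Weekly dose by level.** Level 0: 60 × 2 = 120 mg. Level -1: 50 × 2 = 100 mg. Level -2: 40 × 1 = 40 mg. Level -3: 30 × 1 = 30 mg.

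**Recurrent diarrhea: restart dose under each table (mg/week)**

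| Level before event | Dose before | Table 3 row | Table 2, reduced level | Row ÷ Table 2 |
|---|---|---|---|---|
| 0 | 120 | 50 × 2 = 100 | 50 × 2 = 100 | 1.0 |
| -1 | 100 | 40 × 2 = 80 | 40 × 1 = 40 | 2.0 |
| -2 | 40 | 30 × 2 = 60 | 30 × 1 = 30 | 2.0 |
| -3 | 30 | level -4: stop | stop | – |

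From level -1 the row leaves 80/100 = 0.8 of the previous weekly dose and Table 2 leaves 40/100 = 0.4. Per cycle that is 80 × 3 = 240 mg against 40 × 3 = 120 mg. From level -2 the row gives 60/40 = 1.5 times the previous dose and Table 2 gives 30/40 = 0.75. The 1.5 assumes that the patient was on the Table 2 schedule for level -2. A patient already on 40 mg twice weekly under the row would go from 80 to 60.

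**First-episode Grade 2 diarrhea and moderate bilirubin rows, read literally.** At levels 0 and -1 the restart returns the same weekly dose (120 and 100 mg). At -2 and -3 the once-weekly step changes nothing (40 stays 40, 30 stays 30), and a literal twice-weekly restart gives 80 and 60 mg, twice the previous dose.

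**Reach.** Section 3.2 puts the end of enrolment in June 2016, section 3.1 asks for treatment to start within two weeks of enrolment, and Selinexor is limited to 1 year. If the last patient enrolled on 30 June 2016 and started by 14 July 2016, a 1-year limit counted from cycle 1 ends on 14 July 2017. That is 182 days after protocol version 3.1 (13 January 2017). Counted from the end of two induction cycles it is 182 + 56 = 238 days.

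**The case against.** **Re-escalation rule.** Section 6.3.1 allows re-escalation where the entry for the specific toxicity provides for it, and it permits changes of schedule as well as dose. On that basis the diarrhea row could be meant to set the frequency after resolution. One feature of the row supports this: under Table 2, the interim step at level -2 (40 mg once weekly) and the resumed dose would be identical, so the restart clause would do nothing. The argument makes 40 mg twice weekly a possible intention, but it does not remove the conflict. The rule sends the reader back to the same row, and that row says the restart is at the reduced level, which Table 2 defines as once weekly. Section 6.3 does not settle it either, since it offers a lower dose or once-weekly dosing as alternatives. Nor does the note under Table 3 on the worst preceding toxicity, which gives no frequency.

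**Rows for first-episode diarrhea and bilirubin.** A reader might infer that these rows order a doubled dose at levels -2 and -3. The documents do not support that. An instruction to go down to once weekly presupposes a patient on twice-weekly dosing, and restarting at the current level can mean staying once weekly. These rows are unclear for once-weekly patients, and no more than that.

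**Practical harm.** From level -1 both readings lower the dose. Even the higher restart doses (80 and 60 mg/week) are below level -1 (100) and the starting dose (120), which section 6.3 places below the maximum tolerated dose. The diarrhea row applies only when anti-diarrheal treatment is already maximal, section 6.5.6 describes diarrhea as mostly Grade 1, and the hepatic rows are labelled rare. Section 6.3 also permits flexible reductions, so no site is forced to escalate. All of this stands and keeps the point minor.

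**Conclusion.** There is a minor internal inconsistency in a dosing rule. For recurrent diarrhea, the Table 3 row and Table 2 cannot both be followed from level -1 (80 versus 40 mg/week) or from level -2 (60 versus 30). From level 0 there is no conflict. The first-episode diarrhea and moderate bilirubin rows are ambiguous for patients on once-weekly dosing. The Grade 3/4 rows inherit both problems by referring back.

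A reader might infer that patients were overdosed, or that the lowest levels are easily reached. The documents show no patient at level -2 or -3. From the level 0 start, two one-level reductions or a single two-level reduction reach only -2; level -3 needs a further step. Section 5 of the SAP puts 15 patients on the flat 60 mg regimen from which Table 2 starts, and the documents do not say whether the other patients moved to it. With enrolment closed in June 2016, the reach is small and possibly nil. The timing figures rest on the assumed dates. The primary endpoint, the hypothesis test and the sample size are unaffected.

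**What to change.** 1. In the recurrent-diarrhea sentence, write: *resume at the dose and frequency of the reduced level in Table 2*. The medical monitor should first confirm that Table 2 governs. If the row was intended, write *40 mg twice weekly* there and state that it departs from Table 2.
2. In the first-episode Grade 2 diarrhea and moderate bilirubin rows, replace the twice-weekly restart with: *resume at the dose and frequency of the current level in Table 2*.

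I would not add a general ban on going above the level held before the event. It would clash with the re-escalation rule and with the hyponatremia row, which returns a patient to the starting dose after a first asymptomatic Grade 3 event.

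The cost is three phrases, with no new procedures or data. The clinical downside is that, if Table 2 governs, a level -1 patient with recurrent diarrhea receives 40 instead of 80 mg/week, which is why the medical monitor must decide. If the change is classed as substantial, section 12 requires approval before it takes effect, which uses up part of any remaining treatment time.
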